## Methodology

At all sites, patient recruitment will occur through the following methods: identifying eligibility in medical records, in-house advertising, external community-based advertising, and use of the CHOIR database at Stanford University. Study coordinators will review the clinic schedule daily to identify eligible patients based on pain and opioid information available in the electronic medical record. Clinicians will discuss EMPOWER with patients and obtain permission from interested patients to be contacted by study staff. Study coordinators will then obtain informed consent and register participants in the CHOIR research learning health system database to initiate survey deployment. After completing the baseline survey, participants will be randomized to one of three intervention arms: (1) EMPOWER Taper Only (no behavioral treatment); (2) EMPOWER Taper + pain-CBT; or (3) EMPOWER Taper + CPSMP. Block randomization with variable block sizes, stratified by study site, will be utilized. The Executive Research Team, including the Principal Investigator and the data analytic team, will remain masked to intervention assignment throughout recruitment, enrollment, and data collection. Participants, EMPOWER clinicians, and study coordinators will be aware of intervention assignment. For the study flow diagram, see Figure 1.

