**Figure 1. Study Flow Diagram**

**Eligibility Criteria.** Inclusion criteria are: adults aged 18–85 years, diagnosed with chronic non-cancer pain (lasting at least six months), and actively taking prescription opioids (at least 10 MEDD) for at least three months at any of our seven study sites. Eligibility will not be restricted to specific pain conditions. Exclusion criteria include: clinician-determined moderate or severe opioid use disorder (OUD) as defined by a brief screening tool; inability to provide informed consent; inability to meaningfully participate in group interventions (e.g., due to cognitive impairment or lack of English fluency); or known disruptive behavior that could interfere with the group learning experience and treatment outcomes for the cohort. Patients with moderate to severe OUD will be referred for addictionology consult or triaged per local systems.

Patients with active substance use disorder (SUD) may enroll and local systems will refer them for SUD evaluation and treatment as clinically indicated. No special vulnerable populations will be recruited (e.g., children or patients pregnant at the time of enrollment). All research procedures will take place at the seven clinical sites, with data collection and some treatment elements occurring online.

**Consent Procedures.** Electronic consent will be administered through CHOIR^1 following completion of the screening visit. Participants will provide consent by entering their full name and date on the consent form webpage in CHOIR after reviewing the form with study staff. A copy of the consent form will be securely emailed to the participant. Two study sites (Phoenix Veterans Affairs Health Care System and Kaiser Permanente Oakland) will administer consent locally.

**Participant Compensation.** Participants will receive a \$25 Amazon gift card code for completing assessments at baseline, month 6, and month 12, and \$5 for completing weekly surveys from weeks 1–24 and monthly surveys from months 7–11 (29 total surveys). Total possible compensation for study participation is \$220. For participants who do not complete their 12-month survey and do not respond to any of the contact attempts made by the study team including the EMPOWER clinician we will offer an additional \$50 incentive for completing the last survey.

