***Monthly CHOIR surveys:*** Patients will be assessed monthly for satisfaction with the study, current opioid use, hospital or emergency medical visits, depressive symptoms, suicidality, and other factors that may indicate symptom worsening and require follow-up. Suicidality will trigger e-alerts to the prescribing clinician, site director, site coordinator, study manager, and the overall principal investigator. Site-specific messages will provide patients with instructions for non-emergency triage (e.g., calling the clinic for telephone or in-person follow-up) and emergency triage options in their community (e.g., calling 911), rapid contact with clinic staff, and crisis hotlines.

Weekly and monthly surveys will ensure careful monitoring of patients, triage of issues, and close connections with study staff and prescribing providers to enable rapid taper adjustments and address any additional needs. Study clinicians may securely access EMPOWER CHOIR via a web browser to review patient responses and coordinate participant activities. Comprehensive patient-reported survey batteries will be administered at baseline and at six and 12 months, including data on opioid use.

***Randomization.*** Each site will conduct a site-specific randomized controlled trial using a randomized design, allowing rapid accrual of patient cohorts (N=8–18 per cohort) assigned to the same intervention arm and timely delivery of behavioral interventions. Patients entering the study will be automatically assigned to the currently open intervention arm. The ordering of intervention arms will remain blinded to patients and clinicians, who cannot choose or direct group assignment. Study coordinators, while unblinded, will be trained to maintain clinician and patient blinding. After enrollment and baseline measures, group assignments will be revealed to participants. A statistician unaffiliated with patient care will create unique randomization schemes for each site, enabling prompt receipt of behavioral interventions for those assigned to such arms (ideally within two to ten weeks of taper initiation). Behavioral intervention timing will be recorded.

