#### **Statistical Analysis Plan**

*Aim 1:* Reduce or contain prescription opioid use while maintaining pain control.

*Hypothesis 1a:* We will estimate the proportion of patients achieving patient-centered opioid taper success and test whether this proportion exceeds 40% (treatment success estimate derived from Darnall et al.). We will estimate the binomial proportion of patients with opioid taper success and use the exact test to test whether the proportion is greater than 40%.

*Hypothesis 1b:* We will compare opioid tapering success rates among patients in different initial opioid dose categories: Low (10–49 MEDD), Moderate (50–89 MEDD), High (90–199 MEDD) and Super-High ( $\geq 200$  MEDD).

**Aim 2:** Examine the balance in key patient characteristics such as initial opioid dose, pain intensity, and functional measures separately for the three interventions arms. We will use Chi-square or Fisher's exact tests to compare success rates between opioid dose groups.

***Hypothesis 2a:*** We will compare the intervention success rate of 500 patients in behavioral intervention arms (pain-CBT and CPSMP) with 250 patients receiving patient-centered opioid tapering only (no behavioral intervention; Taper Only). We will use a Chi-square test to compare the success rate between groups. We will apply logistic regression to adjust for baseline covariates.

***Hypothesis 2b:*** We will estimate the difference in intervention success rates between pain-CBT and CPSMP arms using an intention-to-treat procedure and construct 95% CIs for the difference.

***Hypothesis 2c:*** We will compare changes in pain intensity, pain interference, and depression scores (baseline to 12 months) between the pain-CBT and Taper Only as well as between the pain-CBT and CPSMP arms using two-sample t-tests. We will apply an analysis of covariance based on multiple regression to adjust for baseline covariates.

***Hypothesis 2d.*** We will compare improvements in satisfaction with social roles and activities, and self-efficacy for Taper + CPSMP against Taper + pain-CBT and Taper Only.

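### Coordinators who screen and consent patients appear to know which arm is open, and the adjusted 2a model is neither specified nor made the deciding analysis

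*Combined protocol and SAP*

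**What the plan says.** **Allocation.** The Randomization paragraph (under Methodology) has each site accrue cohorts of 8–18 patients to a single arm: "Patients entering the study will be automatically assigned to the currently open intervention arm". On concealment it says: "The ordering of intervention arms will remain blinded to patients and clinicians, who cannot choose or direct group assignment". Coordinators are treated separately: "Study coordinators, while unblinded, will be trained to maintain clinician and patient blinding". Participants learn their arm after enrolment and baseline measures.

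**Who recruits.** The opening of Methodology says: "Study coordinators will review the clinic schedule daily to identify eligible patients". Clinicians then raise the study with the patient and get permission for staff contact. After that: "Study coordinators will then obtain informed consent and register participants in the CHOIR research learning health system database".

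**Other accounts of allocation.** The same Methodology paragraph describes blocks of varying size, stratified by site, with randomization after the baseline survey. The Learning Health System and Informatics Platform section lists automatic randomization after enrolment among CHOIR's functions. Neither mentions a currently open arm.

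**Analysis of 2a.** The Statistical Analysis Plan says under Hypothesis 2a: "We will use a Chi-square test to compare the success rate between groups". The next sentence adds a logistic regression on baseline covariates, without listing them. The paragraph after Hypothesis 2d names Fisher's exact test for the same comparison. Under Aim 2 the plan also checks balance by arm in initial opioid dose, pain intensity and functional measures.

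**The concern.** When one arm is open at a site and its identity is known, choosing whom to process this week is in effect choosing that patient's arm, however automatic the assignment step. Training coordinators to keep the arm from others protects clinicians and patients from that knowledge. It does not stop the coordinators' own knowledge from affecting recruitment.

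This need not be deliberate. One exclusion is a matter of judgement and refers to groups: "known disruptive behavior that could interfere with the group learning experience". It applies to every entrant, but matters most in practice when a group arm is open. The plan does not say who applies it. The SAP also reports groups averaging about 4 participants against the planned 8–18, so there may be pressure to fill them.

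If better-prognosis patients entered more often while a behavioral arm was open, 2a would show a benefit that treatment did not cause. An unadjusted Chi-square or Fisher test passes that difference straight into the p-value.

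**Working it through.** **1. Do coordinators know the arm before consent?** The plan does not say so literally. Methodology says participants, clinicians and coordinators are all aware of assignment. Once the arm is revealed, then, there is no blinding of clinicians or patients left to maintain. The Randomization paragraph contrasts unblinded coordinators with blinded clinicians and patients, and that contrast makes sense only before the reveal. Prior knowledge is therefore a strong inference, not a stated fact.

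**2. The plan's own figure.** Sample Size Calculations gives 80% power for 40% v 53.5% at two-sided 0.05 with 163 per arm. Hypothesis 2a pools two behavioral arms, so the comparison is 2 × 163 = 326 v 163.

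- Pooled rate: (163 × 0.40 + 326 × 0.535)/489 = 0.490
- Null SE: sqrt(0.490 × 0.510 × (1/163 + 1/326)) = 0.0480
- Alternative SE: sqrt(0.40 × 0.60/163 + 0.535 × 0.465/326) = 0.0473
- Power: Φ((0.135 − 1.96 × 0.0480)/0.0473) = Φ(0.867) = 80.7%

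The stated power reproduces and is not in dispute. It confirms 326 v 163 as the relevant sizes.

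**3. What a spurious difference would do.** The documents give no input for the size of any steering, so these are assumptions. Suppose success differs by 20–30 points between easier and harder patients, and the patient mix differs by 10–20 points between behavioral and Taper Only cohorts. The spurious difference is the product: 0.20 × 0.10 = 2 points, 0.20 × 0.20 = 4 points, 0.30 × 0.20 = 6 points.

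With no true effect and 45% success, SE = sqrt(0.45 × 0.55 × (1/163 + 1/326)) = 0.0477. The two-sided rejection probability is Φ(−1.96 + b/SE) + Φ(−1.96 − b/SE).

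| Spurious difference b | b/SE | False-positive rate |
|---|---|---|
| 0 | 0 | 5% |
| 2 points | 0.42 | 7.0% |
| 4 points | 0.84 | 13.4% |
| 6 points | 1.26 | 24.2% |

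**4. How much adjustment can repair.** A simulation (1,500 runs, 326 v 163, no treatment effect) used a binary prognostic factor with 60% v 20% success and a 20-point difference in mix, which gives 0.40 × 0.20 = 8 spurious points. These inputs are also assumed.

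| Analysis | Rejection rate |
|---|---|
| Unadjusted | about 39% |
| Logistic, factor measured perfectly | 4.6% |
| Logistic, factor measured with 80% accuracy | about 20% |
| Logistic, uninformative proxy | about 39% |

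Adjustment removes only the part of the bias that well-measured covariates carry.

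**The case against.** There are several fair points on the other side.

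- **Adjustment is planned.** A reader who stops at the Chi-square sentence might infer that 2a has no covariate adjustment. The next sentence plans a logistic regression, so that reading fails. What stands is that its covariates are not listed, site (the stratification factor) is not named, and nothing says which analysis decides 2a.
- **Coordinators do not control recruitment.** Clinicians, blind to arm order, make the first approach. Patients also come through in-house and community advertising, and assignment is automatic. This stands as a limit: coordinators' influence is over who is put forward and when they are contacted and consented.
- **The scheme may be less exposed.** If allocation follows the Methodology blocks or CHOIR's post-enrolment step, the opportunity is much smaller. This stands until the accounts are reconciled, but the Randomization paragraph is the most specific of the three.
- **Balance is already checked.** True for enrolled patients. No log of eligible or approached patients, or of consent rates by open arm, is described.
- **The size is assumed.** Correct. Reaching 13–24% needs steering in a consistent direction across sites with separate randomization schemes, and zero bias is equally compatible with the documents.

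**Conclusion.** The concealment gap holds on the Randomization paragraph as written: arm order is hidden from patients and clinicians, but not from the staff who screen and consent. It rests on reading coordinators as unblinded before consent, and on that paragraph being the scheme in use.

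On the analysis side, the defect is an adjusted 2a model left unspecified and unranked beside two unadjusted tests.

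The figures of about 7%, 13% and 24% depend wholly on assumed spurious differences of 2, 4 and 6 points. A reader might infer from them that enrolment was steered or that 2a is biased. The documents show an opportunity and no evidence of either. Nor should one infer that an adjusted model would settle the matter, since motivation and likely group engagement may not be measured. The point is worth acting on because 2a is the main comparison of behavioral treatment with Taper Only and part of the remedy is cheap.

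**What to change.** 1. **Reconcile the allocation text.** State one scheme across Methodology, the CHOIR section and the Randomization paragraph, and say when coordinators learn the arm.
2. **Mask coordinators until assignment.** In the Randomization paragraph, have CHOIR show the arm to coordinators only after consent and the baseline survey are submitted, and keep cohort switch points hidden from sites. This is partial: once the first patient in a cohort is told, the arm can be guessed, and up to 7 of 8 (88%) or 17 of 18 (94%) of a cohort enter after that patient. Coordinators also get less notice for booking groups against the two-to-ten-week target. The virtual-format section shows enrolment already under way, so masking helps only patients still to enter.
3. **Log recruitment.** Record eligible and approached patients by date and open arm, and report consent rates by open arm beside the balance table already planned. The cost is a screening-log field.
4. **Name the deciding 2a analysis.** In the Statistical Analysis Plan, make it the logistic regression adjusted for site, baseline MEDD and baseline pain, with one unadjusted test as supportive. Use calendar period only in a sensitivity analysis, with periods defined in advance, because filling one arm at a time partly confounds period with arm. State that adjustment does not correct selection on unmeasured traits such as motivation. The cost is SAP wording, to be settled while the analytic team is still masked.

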### ***Study Outcomes***

#### ***Primary Outcome (Aim 1) – Taper Success at 12 months***

Taper success will be defined as a  $\geq 50\%$  reduction in MEDD from baseline to 12 months without significant pain intensity increase ( $\leq 1$ -point increase) or no opioid increase with significant pain relief ( $\geq 2$ -point decrease in pain intensity). Please see Appendix A, Data Measurement Plan, for more details.

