## Project Summary

The purpose of this pragmatic clinical trial is to transform care, reduce health risks, and improve outcomes for patients with chronic pain who are taking long-term prescription opioids. Our proposed study will address several critical evidence gaps that currently hinder patients and physicians from making informed decisions about pain care. This project will provide both patients taking opioids and their prescribers with the specific evidence needed to choose the most effective strategies for reducing opioid doses and minimizing pain, reducing pain interference, and improving role function.

For patients interested in reducing opioid use, we aim to: (1) reduce prescription opioid use while maintaining pain control; and (2) compare the effectiveness of the Chronic Pain Self-Management Program (CPSMP), cognitive behavioral therapy for chronic pain (pain-CBT), and no behavioral treatment, all within the context of patient-centered collaborative opioid tapering. The acronym EMPOWER stands for *Effective Management of Pain and Opioid-Free Ways to Enhance Relief*.

[Please note: Along with the EMPOWER randomized controlled trial, PCORI funded a separate sub-study involving a national observational study of people taking daily prescription opioids (not tapering). As this observational sub-study was not part of the randomized controlled trial, it is not described in this protocol.]

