## Study Goals and Objectives

### *Aim 1: Reduce or Contain Prescription Opioid Use While Maintaining Pain Control.*

Hypothesis 1a. At one year, 40% of participants in the Taper Only group (no behavioral treatment) will successfully reduce prescription opioids by  $\geq 50\%$  in MEDD without worsening pain intensity, pain interference, or satisfaction with social roles and activities at 12 months.

Hypothesis 1b. Success with patient-centered opioid tapering will not be associated with the starting MEDD.

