### *Aim 2: Compare the Effectiveness of (1) Taper + CPSMP, or (2) Taper + pain-CBT, or (3) No Behavioral Treatment (Taper Only) within the Context of Patient-Centered Collaborative Opioid Tapering.*

Hypothesis 2a. Participants receiving behavioral interventions (Taper + pain-CBT or Taper + CPSMP) will be more likely to reduce their opioid dose than those in the Taper Only group (no behavioral intervention).

Hypothesis 2b. There will be no significant differences in dosage reduction or the percentage of participants reducing dosage between the Taper + pain-CBT and Taper + CPSMP groups.

Hypothesis 2c. Participants in the Taper + pain-CBT group will experience less pain, less pain interference, and decreased depression compared to those in the Taper + CPSMP or Taper Only groups.

Hypothesis 2d. Participants in the Taper + CPSMP group will show greater improvements in satisfaction with social roles and activities and self-efficacy compared to those in the Taper + pain-CBT or Taper Only groups.

*Exploratory Hypothesis 2e.* Opioid escalation will be less common among participants in the behavioral intervention groups (Taper + pain-CBT or Taper + CPSMP) compared to those in the Taper Only group.

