#### ***Secondary Outcomes (Aim 2) – Pain Characteristics for the Three Intervention Arms at 12 months***

Taper success (MEDD and pain intensity), pain interference, pain self-efficacy, and depression and satisfaction with social roles and activities will be assessed (for more details, see Appendix A). Specifically, depression and satisfaction with social roles and activities will be assessed using National Institutes of Health PROMIS short-form measures which are commonly used in pain research. These domains were identified by the Initiative on Methods, Measurement, and Pain Assessment in Clinical Trials as core outcomes. Web-based PROMIS assessment center software will calculate short-form T scores using Item Response Theory scoring algorithms that apply the Bayesian expected a posteriori method.

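### H2a and H2b claim opioid dose reduction but are tested only on a taper-success composite that pain change alone can move, and H1a states a different event from the one tested

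*Combined protocol and SAP*

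**What the plan says.** All references are to the combined protocol and SAP.

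- **Primary Outcome (Aim 1).** Success is a MEDD reduction of at least 50% with a pain increase of no more than 1 point, "or no opioid increase with significant pain relief" (a fall of at least 2 points).
- **Study Goals, Aim 1.** The aim is titled "Reduce or Contain Prescription Opioid Use While Maintaining Pain Control". H1a requires a reduction of at least 50% "without worsening pain intensity, pain interference, or satisfaction with social roles and activities at 12 months". It has no pain-relief route.
- **Study Goals, Aim 2.** H2a says that participants in the behavioral arms "will be more likely to reduce their opioid dose than those in the Taper Only group". H2b expects "no significant differences in dosage reduction or the percentage of participants reducing dosage" between the two behavioral arms. H2c predicts less pain with pain-CBT than in either other arm.
- **Sample Size Calculations and Statistical Analysis Plan.** H1a, H2a and H2b are powered on the taper success rate and analyzed as success proportions.
- **Secondary Outcomes (Aim 2).** MEDD appears only inside the composite: "Taper success (MEDD and pain intensity), pain interference, pain self-efficacy" and so on. The mixed-model outcome list in the Statistical Analysis Plan names pain intensity but not MEDD.

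**The concern.** A hypothesis about dose should be answered by an endpoint that moves only when dose moves. Here pain intensity is a condition in both routes, and one route needs no reduction at all. The mismatch runs both ways. A participant with a 30% reduction and stable pain has reduced the dose but is a failure; one with an unchanged dose and 2 points of relief is a success.

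The plan itself expects pain to differ by arm. H2c says so for pain-CBT, and the Study Arms section expects both behavioral interventions to help patients manage pain. If pain improves and dose does not, H2a could be reported as a dose benefit. H2b could appear contradicted although doses were the same. The separate comparison of pain intensity would show a pain gain, but not how much of the success difference it explains.

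H1a has a related problem: the proportion tested against 40% is not the proportion that the hypothesis describes.

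**Working it through.** **1. The plan's own figures, all for the composite.**
- H2a: 53.5% v 40% with 326 pooled behavioral v 163 Taper Only. Pooled rate (326×0.535 + 163×0.40)/489 = 0.49. Null SE = √[0.49×0.51×(1/326+1/163)] = 0.0480; alternative SE = √[0.535×0.465/326 + 0.40×0.60/163] = 0.0473. Power = Φ[(0.135 − 1.96×0.0480)/0.0473] = 0.81. This matches the stated 80%. (163 v 163 would give 69%, so the figure is for the pooled contrast.)
- H2b: 1.96×√(2×0.25/163) = 0.109, matching ±11%.
- H1a: the exact test needs 79 of 163 (upper tail 0.0173 at 40%); P(X ≥ 79 | 51.5%) = 0.803, matching 80%.

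**2. Is dose reduction compared between arms anywhere else?**

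| Place | Content | Isolates reduction? |
|---|---|---|
| Secondary Outcomes (Aim 2) | MEDD as a component of taper success | No |
| Mixed-model outcome list | Pain, interference, depression, self-efficacy, roles | No |
| Exploratory H2e | Escalation by arm | No |
| Sensitivity Analysis | Threshold moved from 50% to 30% | No; not stated whether the pain-relief route stays |

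No between-arm analysis of MEDD change or of a dose-only proportion is specified.

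**3. How far can pain alone move H2a and H2b?** The documents give no route frequencies, so these inputs are assumed: in every arm 40% reach a reduction of at least 50% and 80% have no increase; pain change is normal with SD 2, rounded to integers, and independent of dose; its mean is zero in Taper Only; there is no dose effect. With mean pain benefit δ:

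- reduction route = 0.4×Φ[(1.5+δ)/2]
- relief route among the others without an increase = (0.8−0.4)×Φ[(δ−1.5)/2]

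| δ | Reduction route | Relief route | Success |
|---|---|---|---|
| 0 | 0.309 | 0.091 | 0.400 |
| 0.622 (0.311 SD, the plan's detectable difference) | 0.342 | 0.132 | 0.474 |
| 1 (assumed) | 0.358 | 0.161 | 0.518 |

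Rejection probabilities come from exact enumeration: uncorrected chi-square for H2a (326 v 163) and Wald 95% CI excluding zero for H2b (163 v 163, pain-CBT alone benefiting).

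| | 0.311 SD | 1 point |
|---|---|---|
| H2a, pain-CBT alone benefits (H2c) | 12% | 23% |
| H2a, both behavioral arms benefit | 34% | 70% |
| H2a, both arms, no pain limit on the reduction route | 14% | 31% |
| H2b CI excludes zero | 27% | 58% |
| H2b, no pain limit on the reduction route | 12% | 25% |

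A dose-only endpoint, at least 50% reduction regardless of pain, gives 5% in every case.

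Sensitivity at 0.311 SD (pain SD 1.5 to 2.5, 20 to 40% reducers, 70 to 90% with no increase): H2a 8–18% with pain-CBT alone benefiting and 19–54% with both arms.

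**4. H1a.** Read with the same 1-point pain limit, the stated event is a subset of the tested one: it drops a route to success and adds two conditions. If every success in a 51.5% group came by the reduction route and 10% of them worsened on interference or roles, the stated event rate is 0.515×0.90 = 46.4%, and P(X ≥ 79 | 46.35%) = 0.32.

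**The case against.** The composite is a reasonable outcome. The Aim 1 title covers containing as well as reducing opioid use, and the pain limit on the reduction route carries out the purpose in the Project Summary to "reduce prescription opioid use while maintaining pain control". That stands. Part of the shift calculated above is therefore intended, and this is why the rows without that limit are shown. A reader might infer that the primary outcome is invalid or the sample size wrong; the documents support neither.

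The secondary-outcome list is introduced as an inclusion list, and the naming of MEDD beside taper success could signal that it will be summarized by arm. So it would go too far to say that MEDD will not be compared. What stands is that no such comparison is specified.

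A reader might also take the 70% figure as the likely risk of a false dose claim. It needs a 1-point benefit in both behavioral arms, a size that the documents do not give. H2c concerns pain-CBT alone, and at the plan's own detectable difference that gives 12%. Independence of pain and dose is assumed too, and was not varied; an individualized taper makes it doubtful.

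For H2b, the Statistical Analysis Plan uses the CI to judge equivalence but gives no margin. Exclusion of zero is taken from the hypothesis wording, which speaks of no significant differences.

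**Conclusion.** The mismatch rests on the text and holds without any simulation: H2a and H2b claim dose reduction, while the specified tests concern an outcome that an unchanged dose can satisfy. The size is illustrative. At 0.311 SD with no dose effect, H2a rejects 12% of the time if pain-CBT alone benefits and 34% if both behavioral arms do, and the H2b interval excludes zero 27% of the time, against a nominal 5%. These figures show the mechanism and a plausible order of size under assumed frequencies; they do not predict the trial's result.

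For H1a, the tested rate can overstate the stated event. It might be inferred that this matters only if the pain-relief route is common. That does not follow, because the two added conditions lower the stated event rate whatever the frequency of that route: 46.4% and 32% power in the example, where the 10% is assumed.

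This should be fixed before analysis. The stated power and precision need no correction as figures for the composite.

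**What to change.** 1. Keep the composite as a named outcome, and tabulate successes by route and arm.
2. For H2a and H2b, either (a) prespecify between-arm comparisons of percent MEDD change, the proportion with any reduction, and the proportion with at least 50% reduction regardless of pain; or (b) reword both hypotheses to claim composite taper success only.
3. Reconcile H1a with the Primary Outcome, Sample Size and Statistical Analysis Plan sections so that it states the event tested, and say which definition the 40% benchmark refers to. If H1a's wording is kept, define worsening of pain interference and role satisfaction.
4. State whether the 30% sensitivity definition keeps the pain-relief route.

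**Cost.** No new data are needed: the comprehensive surveys are given "at baseline and at six and 12 months, including data on opioid use". Option (b) needs wording only. Option (a) adds two or three comparisons to a plan without multiplicity correction, and the stated 80% power does not carry over to them. With 326 v 163, 80% power needs about (1.96+0.84)×√(1/326+1/163) = 0.27 SD for percent MEDD change; 73% v 60% or 81% v 70% for any reduction; and 32% v 20%, 43% v 30% or 53% v 40% for at least 50% reduction. The control rates are assumed.
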